Questionnaire responses will be entered via a custom designed redcap data entry form and checked for completeness by research personnel.

From these questionnaires, we will place each participant, as on another protocol approved by this IRB, on a continuum that describes their general

[figure not shown]

Figure 4: The dimensional structure of the continuum of cognitive style to be used, including psychosocial constructs associated with each end.

cognitive style. We will use multidimensional scaling (MDS) to force catastrophizing and optimism as 2 ends of this continuum (Figure 4). These two constructs describe cognitive styles that are strongly inversely associated with each other; MDS will provide the optimal weights to best order individuals on this latent scale. Studies have examined the interplay of these constructs with other psychological concepts such as acceptance, pain-related disability and psychosocial adjustment and have found that both are reliably associated with the positive and negative aspects of the adjustment to pain.

Subjects will be trained and provided with a tablet device for daily diary entries and the accelerometer. The accelerometer has wireless connectivity such that daily diary and activity will be time stamped and can be easily uploaded by the patient to the data coordinating center on a regular basis. We will utilize a password protected web based database tool for near real-time access to facilitate adherence (e.g., phone calls or emails when participants fail to wear the device during regularly scheduled time points).

We will have subjects begin using the tablet and wearing the accelerometer approximately 2 weeks prior to surgery so that they will become familiar with the devices to increase compliance and adherence to the protocol after surgery.

We will access PEBL software for cognitive assessment. This open-source software employs several cognitive tasks that look and feel like challenging games that allow the assessment of different areas of cognitive function. The specific tasks will be the Iowa gambling task to assess impulsivity, Wisconsin card sorting task to assess executive function, and the TSK to assess kinesiophobia. Participants will complete these tasks at baseline and again when returning to the HPRU 2 months after surgery, when they will return the electronic tablet and the accelerometer.

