Statistical Power Considerations. Enrolling $N = 120$ participants ($n = 60$ per study arm) provides sufficient power to examine the study's primary hypothesis. Assuming that each individual contributes ~ 60 daily measurements, with $\alpha = 0.05$, $\text{power} = .80$, a modest level of within-subject correlation, and adequate model fits (SD of the residuals < 2.0), we will be able to detect difference in slopes of $d = 0.09$ units. Thus, if the saline group exhibited a mean pain score of 8.0 VAS units after surgery and decreased on average 0.38 points each day (i.e., expected full recovery at 21 days), sufficient power exists to detect an enhanced slope of 0.47 in

the oxytocin group (i.e., expected full recovery in ~17 days). This difference is a clinically meaningful effect size that could substantially improve the life of patients.

Outcome measures.

Primary outcome measure: Modeled trajectory of recovery from pain (worst daily pain intensity) using a log of time form.

Several secondary analyses are planned, including slope of modeled change in other pain intensity measures (daily average pain and pain right now), activity and cognitive function tests. Interaction between preoperative cognitive style and slope of modeled change in these measures. that examine changes in cognition (e.g., impulsivity, attention) as well as kinesiphobia. The cognition measures (Iowa gambling task, Wisconsin card sort, TSK) collected at baseline and 2 months after discharge will be examined using generalized linear model with time as a fixed factor.

Human subjects protection.

Subject recruitment methods. Appropriate subjects will be identified and approached in the Department of Orthopedics during their regular scheduled appointment, by research personnel. Research personnel will utilize a private exam room to talk with subjects. Subjects will be given the study details and the opportunity to read the informed consent. The subject may take the informed consent home and make their decision regarding study participation. Contact information for the research staff will be provided to the subject so that they may call for questions or to participate. Study personnel will make every effort to approach any subject that will be scheduled for primary HA.

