Study objective: The primary objective is to determine the effectiveness of intrathecal oxytocin to speed recovery from pain, as measured by growth curve modeling, after TKA.

Secondary objectives are:

- a. To determine the effectiveness of oxytocin to speed gain in activity, assessed by actigraphy and analyzed by growth curve modeling, after TKA
- b. To determine the effectiveness of oxytocin to speed recovery from self-assessed disability, as measured by growth curve modeling, after TKA
- c. To determine the effectiveness of oxytocin to hasten time to cessation of opioid use, as measured by growth curve modeling, after TKA

Section 3: Trial Methods

9. *Trial design*

The trial is a single center, randomized, parallel-group, placebo-controlled trial. Treatment allocation is a 1:1 ratio. Patients are randomized to either oxytocin or saline control.

10. *Randomization*

Participants were randomized into treatment arms in a 1:1 ratio using permuted blocks of sizes 4 to 8. Randomization assignments. The ‘blockrand’ package in R was used by the study statistician. Allocation concealment was maintained using a centralized pharmacy administration of study drug. Both study agents are designed to look identical to each other to maintain blinding.

11. *Sample size*

Enrolling $N = 120$ participants ($n = 60$ per study arm) provides sufficient power to examine the study’s primary hypothesis. Assuming that each individual contributes ~ 60 daily measurements, with $\alpha = 0.05$, power = .80, a modest level of within-subject correlation, and adequate model fits (SD of the residuals < 2.0), we will be able to detect difference in slopes of $d = 0.09$ units. Thus, if the saline group exhibited a mean pain score of 8.0 VAS units after surgery and decreased on average 0.38 points each day (i.e., expected full recovery at 21 days), sufficient power exists to detect an enhanced slope of 0.47 in the oxytocin group (i.e., expected full recovery in ~ 17 days). This difference is a clinically meaningful effect size that could substantially improve the life of patients.

12. *Framework*

Superiority testing will be used to examine differences between the treatment arms.

13a. *Information on interim analyses*

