The level of consent withdrawal will be tabulated (classified as “consent to continue follow-up and data collection” “consent to continue data collection only”, “complete – no further follow-up or data collection”).

24b. *Timing of withdrawal/lost to follow up data*

This will be presented in CONSORT diagram format rather than as a table, with numbers and reasons for withdrawal and/or exclusion from analysis given at each stage

24c. *Reasons for withdrawal/lost to follow up data*

The numbers (with reasons, if available) of losses to follow-up (drop-outs and withdrawals) over the course of the trial will be summarized by treatment arm.

25a. *List of baseline characteristics to be summarized*

Patients will be described with respect to age, sex, race, ethnicity, medications, number of painful conditions excepting the hip and their locations, questionnaire and cognitive game scores, baseline pain and activity from the daily diaries prior to surgery, attending surgeon, and surgical approach (anterior vs posterior).

25b. How baseline characteristics will be described

Categorical data will be summarized by numbers and percentages. Continuous data will be summarized by mean, SD and range if data are normal and median, IQR and range if data are skewed. Minimum and maximum values will also be presented for continuous data. Tests of statistical significance will not be undertaken for baseline characteristics; rather the clinical importance of any imbalance will be noted.

Section 5: Analysis

26. Outcomes and timings

Primary outcome: Worst pain intensity measured using a 0 to 10 numerical rating scale on a daily diary. Measurements will be obtained each evening from day 0 (surgery) to day 56 after surgery. The pain measurements will be evaluated in a statistical model using an intercept (i.e., immediate pain after surgery) and slope (i.e., rate of change of pain during the observation period).

Secondary outcomes: Daily measurements such as physical activity, as measured via actigraphy, disability, as measured by daily diaries and weekly WHODAS 2.0 scores, and opioid self-administration, as measured by daily diaries will be collected from day 0 (surgery) to day 56 after surgery.

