These individual predictors sets will then be used to test the primary hypothesis that oxytocin alters time course of recovery after TKA. The primary statistical inference will be a likelihood ratio comparing two models estimated with and without oxytocin group assignment. Thus, the pain trajectory model comparing medication assignment (oxytocin versus placebo) adjusted for the covariates of characteristics and preoperative study data will be compared to a similar model without medication assignment using a Chi-squared test. This approach allows a single direct test of the primary hypothesis and will be interpreted using a two-tailed hypothesis test using $p < 0.05$. A statistically significant difference will be interpreted as evidence to support the primary hypothesis that pain trajectory differs between oxytocin and saline treatment.

Secondary analyses: Trajectories for daily activity, as measured via actigraphy, disability, as measured by daily diaries and weekly WHODAS 2.0 scores, and opioid self-administration, as measured by daily diaries, will be analyzed using a similar approach to that of the primary outcome, with one exception. For the activity analysis, preoperative data covariate included will not be pain, but rather degree of daily actigraphy activity and its variance during the two weeks prior to surgery as assessed by daily diaries. For disability analysis, preoperative data covariate included will not be pain, but rather degree of daily disability and its variance during the two weeks prior to surgery as assessed by daily diaries and baseline WHODAS 2.0 score. As noted, with the exception of the PROMIS depression score, other questionnaire and cognitive game scores will be described for the two groups but not analyzed or entered as covariates for the purpose of the primary analysis and publication. Changes in questionnaire data will be evaluated using the generalized linear model regressing follow-up score on baseline score and medication group assignment.

27c. Methods to be used for assumptions to be checked for statistical methods for primary and secondary analyses

The assumptions underlying parametric modeling will be evaluated using regression diagnostic procedures and histograms of residuals.

27d. Alternative methods to be used if distributional assumptions do not hold for primary and secondary analyses

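### Iowa gambling and Wisconsin card sort, a secondary analysis in the protocol, have no between-arm analysis in either document: the protocol's model names only time, and the SAP's regression on arm covers questionnaires only.

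*SAP*

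**What the plan says.** **Protocol.** Under Outcome measures, the planned secondary analyses include "daily average pain and pain right now), activity and cognitive function tests". The same paragraph gives the model for the Iowa gambling task, Wisconsin card sort and TSK (Tampa Scale of Kinesiophobia). Scores "collected at baseline and 2 months after discharge will be examined using generalized linear model with time as a fixed factor". Time is the only factor named. TSK appears twice in the protocol: as a questionnaire in Table 1, and among the computerised tasks under Preoperative procedures ("Wisconsin card sorting task to assess executive function, and the TSK to assess kinesiophobia").

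**SAP.** The secondary objectives (item 8) cover activity, disability and opioid cessation. The secondary outcomes (item 26) begin "Daily measurements such as physical activity, as measured via actigraphy, disability, as measured by daily diaries and weekly WHODAS 2.0 scores" and go on to opioid use. Cognition is in neither list. For the primary publication, item 26 gives questionnaire and game data as summary scores by arm.

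Items 27a/27b, under Secondary analyses, say that, PROMIS depression apart, the other "questionnaire and cognitive game scores will be described for the two groups but not analyzed or entered as covariates". That sentence ends by limiting itself to the primary analysis and publication. The next sentence reads: "Changes in questionnaire data will be evaluated using the generalized linear model regressing follow-up score on baseline score and medication group assignment". It names no scales, does not mention the games, and does not say in which report it will appear.

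**The concern.** A randomised trial collects the two games before surgery and again at about 2 months, and the protocol counts them among its secondary analyses. The question that the design can answer is whether the arms differ at follow-up. A model with time alone answers a different one: whether scores moved on average, in both arms together. They may well move for reasons unrelated to study drug, such as having done the task before, less pain, or less analgesic use. A significant result could then be reported in an oxytocin trial although it carries no information about oxytocin, while a real arm difference could go unseen.

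The later SAP does not supply the missing comparison. It moves the games to description without saying that this departs from the protocol, and its valid regression on arm is worded for questionnaires. If someone later wants a treatment effect on the games, the method would have to be chosen without a pre-specified rule.

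**Working it through.** **1. The rules side by side**

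| Measure | Protocol | SAP, primary publication | SAP, regression on baseline and arm |
|---|---|---|---|
| Iowa gambling | time only | described by arm | not covered |
| Wisconsin card sort | time only | described by arm | not covered |
| TSK | time only; also a Table 1 questionnaire | described by arm | covered as a questionnaire |
| Other questionnaires | repeated at 2 months; no separate model for their change | described by arm (PROMIS depression is also a covariate) | covered, scales not named |

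The first two rows have no arm comparison beyond summary statistics.

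**2. What a time-only model tests**

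Inputs from the documents: 120 evaluable patients, 1:1, so 60 per arm; two-sided 5%. The documents give no SD, retest correlation r or practice effect for these tasks, and no power statement for them. Those values are assumptions below, in SD units. There is no figure in the plan to reproduce on this point.

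SD of change = √(2(1 − r)); z = shift × √120 / SD of change; chance of significance ≈ Φ(z − 1.96). With the same shift in both arms and no drug effect:

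| Common shift | r = 0.5 (SD 1.000) | r = 0.6 (SD 0.894) | r = 0.7 (SD 0.775) |
|---|---|---|---|
| 0.2 SD | z = 2.19, 59% | z = 2.45, 69% | z = 2.83, 81% |
| 0.3 SD | z = 3.29, 91% | z = 3.67, 96% | z = 4.24, 99% |
| 0.5 SD | z = 5.48, about 100% | z = 6.12, about 100% | z = 7.07, about 100% |

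**3. Time-only test against the SAP's regression**

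Simulation of 4,000 trials, 60 per arm, r = 0.5; time-only is a paired test on all 120 patients:

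| Truth | Time-only rejects | Regression on baseline and arm rejects |
|---|---|---|
| No change, no arm difference | 5.4% | 5.2% |
| Common change 0.5 SD, no arm difference | 99.98% | 5.0% |
| Arm difference 0.5 SD, average change zero | 4.2% | 87.8% |

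Check on the last cell: SE = √(2/60) × √(1 − 0.25) = 0.158; 0.5/0.158 = 3.16; Φ(3.16 − 1.96) ≈ 88.5%, in line with the simulation.

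**4. What the regression could detect for the games**

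Detectable arm difference at 80% power = (1.96 + 0.84) × √(2/60) × √(1 − r²):

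- r = 0: 0.51 SD
- r = 0.5: 0.44 SD
- r = 0.7: 0.37 SD

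So the comparison is usable for a moderate effect, but the trial was not sized for it.

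**The case against.** The strongest reply is that the time-only model may never be run. The SAP is the later document, its details were set before unblinding, it does not carry that model forward, and description by arm is itself a rule. Arm means and variances would also let a reader form a rough unadjusted contrast. Further, the protocol says that time is a fixed factor, not that it is the only one, and the sentence before it is visibly incomplete.

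This limits the harm but does not remove the gap. The SAP does not say that it replaces the protocol's cognition analysis. The protocol's wider statement that its models test oxytocin concerns growth curves for pain and movement, not the two-visit tasks. A treatment term for cognition therefore has to be guessed.

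Three stronger readings are tempting, and the documents do not support them.

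- A reader might infer that the two adjacent SAP sentences contradict each other. The first is limited to the primary analysis and publication, and the second carries no such limit. They can be read together, with description in the main paper and regression elsewhere. The scope is unclear, which is less than a contradiction. SAP item 29 lists no additional analyses and no later report is described, so the ambiguity does need settling.
- A reader might infer that no valid rule governs the 2-month endpoints. Regression of follow-up on baseline and arm is a valid randomised comparison for the questionnaires.
- A reader might infer that TSK receives opposite instructions in the SAP because the protocol lists it twice. The SAP schedule has separate rows for the gambling and card-sorting tasks but none for TSK, so there it falls naturally under questionnaires.

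**Conclusion.** The point holds for two measures. Iowa gambling and Wisconsin card sort are part of a protocol secondary analysis, and neither document specifies a between-arm analysis for them. The protocol's model, followed as written, would test average change and not oxytocin. The SAP's move to description is an undeclared departure. The reporting scope of the questionnaire regression is a linked ambiguity.

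The sizes in the working rest on assumed shifts and correlations. The direction does not: without a treatment term, the model cannot estimate a treatment effect.

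A reader might also infer a large false-positive risk from testing all 13 Table 1 questionnaires at 5% (1 − 0.95^13 = 49%). That assumes independent tests of every scale. The documents do not say that every scale will be tested, and SAP item 17 openly declares no adjustment for secondary outcomes. It is not part of this point.

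The matter is worth correcting, but it concerns minor endpoints without a power basis and leaves the primary pain analysis unaffected.

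**What to change.** In SAP items 26 and 27a/27b:

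1. State that the protocol's time-only model for cognition is replaced. For Iowa gambling and Wisconsin card sort, regress the 2-month score on baseline score and treatment arm, and report the arm difference with its 95% confidence interval.
2. State that TSK follows the questionnaire rule.
3. Label these analyses secondary or exploratory and unadjusted for multiplicity. If they are specified after unblinding, label them post hoc.
4. State whether the questionnaire regression belongs to the primary report or a later one, and which scales it covers.

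The cost is a few sentences and a few regressions on data already collected. The downside is some extra unadjusted, unpowered tests: with one score per game, two tests carry a chance of at least one false positive of 1 − 0.95² = 9.75% under independence. If the investigators prefer to keep the games descriptive, they should declare that as a departure from the protocol. The regression is the better choice because it uses the randomised comparison.

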19a. *Definition of adherence to the intervention and how it is assessed*

Compliance is assessed based on the number of daily diary entries after hospital discharge. It is defined as:

$\% \text{ compliance} = (\text{number of entries} / \text{number of days entries were to be completed}) * 100\%$

19b. *How adherence will be presented*

The number and % of participants completing more than 80% of the daily diaries after surgery will be provided by treatment group in a table. All available data will be included in the analysis from the intention to treat sample.

19c. *Definition of protocol deviation*

The following are pre-defined major protocol violations with a direct bearing on the primary outcome:

1) Surgery during the primary outcome assessment period (first 8 weeks after TKA surgery)

19d. *Description of which protocol deviations will be summarized*

Protocol deviations are classified prior to unblinding of treatment. The number (and percentage) of patients with major and minor protocol deviations will be summarized by treatment group with details of type of deviation provided. The patients that are included in the ITT analysis data set will be used as the denominator to calculate the percentages. No formal statistical testing will be undertaken.

20. *Analysis population*

The intention-to-treat population will include all randomized patients who received study drug.

Section 4. Trial Population

21. *Screening data*

Enrollment: The dates of recruitment, the number of patients screened, the number of patients recruited, the number of screened patients not recruited, and the reason for non-recruitment will be reported as part of the CONSORT diagram.

22. *Eligibility criteria*

Inclusion and exclusion criteria are provided in the protocol. The number of ineligible patients randomized, if any, will be reported, with reasons for ineligibility

23. *Information to be reported in the CONSORT flow diagram*

A CONSORT flow diagram (appendix A) will be used to summarize the number of patients who were:

- assessed for eligibility at screening
- eligible at screening
- ineligible at screening*
- eligible and randomized
- eligible but not randomized*
- received the randomized allocation
- did not receive the randomized allocation*
- lost to follow-up*
- discontinued the intervention*
- randomized and included in the primary analysis

*reasons will be provided for post randomization exclusions.

24a. *Description of level of withdrawal*

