If necessary, the primary outcome distribution will be log transformed to satisfy assumptions. For secondary outcomes, the generalized linear model allows the specification of an array of distributions (e.g., normal, binomial, gamma) with corresponding link functions (e.g., log).

27e. Planned sensitivity analyses

Three sensitivity analyses will be performed to evaluate the robustness of the trajectory analysis to the primary and secondary analyses. These are to include multiple imputation for missing data, to include monthly through 6 months and the 12-month daily diary data and to include a change point rather than log of time model, as previously described [2]. Two other sensitivity analyses will be

performed to evaluate the robustness of other causes of variability in trajectory in the primary and secondary analyses: race and surgeon.

27f. *Planned subgroup analyses*

No subgroup analyses are planned.

28. *Missing data – reporting and assumptions/statistical methods to handle missing data*

Multiple imputation will be used to account for embedded missing data in daily diary entries. The autocorrelation of each time-series for each individual along with baseline predictors will be used in conjunction with the MICE algorithm to estimate $m = 20$ imputations. These imputations will then be re-analyzed using the primary model with Rubin's rules used to pool the estimates of model parameters.

29. *Details of any additional statistical analyses required e.g., complier-average causal effect analysis.*

None

30. *Harms*

The number (and percentage) of patients experiencing each AE/SAE will be presented for each treatment arm categorized by severity. For each patient, only the maximum severity experienced of each type of AE will be displayed. The number (and percentage) of occurrences of each AE/SAE will also be presented for each treatment arm. No formal statistical testing will be undertaken

31. *Statistical Software*

The analysis will be carried out using R version 4.1.2

32. *References*

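### The only missing-data sensitivity analysis shares the primary model's missing-at-random assumption, so it says little about dropout that depends on unrecorded pain

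*SAP*

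**What the plan says.** **Primary analysis.** SAP items 27a and 27b specify a hierarchical linear model with an intercept and a ln(time) slope. Item 27b tests treatment by a likelihood ratio: "The primary statistical inference will be a likelihood ratio comparing two models estimated with and without oxytocin group assignment". Item 19b sets the data to be used: "All available data will be included in the analysis from the intention to treat sample".

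**Sensitivity analyses.** Item 27e lists three for the trajectory, beginning "These are to include multiple imputation for missing data, to include monthly through 6 months and the 12-month daily diary data"; the third is a change-point model. Two more concern race and surgeon. Only the imputation is directed at missing data.

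**Imputation.** Item 28 gives the detail: "Multiple imputation will be used to account for embedded missing data in daily diary entries". On the method it says "The autocorrelation of each time-series for each individual along with baseline predictors will be used in conjunction with the MICE algorithm", with 20 imputations, and then "These imputations will then be re-analyzed using the primary model", pooled by Rubin's rules. No offset, pattern-mixture, reference-based or tipping-point element appears. The heading of item 28 mentions assumptions, but the text states none.

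**Dropout.** Item 24c says that "losses to follow-up (drop-outs and withdrawals) over the course of the trial will be summarized by treatment arm". No analysis method is attached to those losses, and neither document gives an expected rate. The protocol (Post-hospital discharge measures) cites more than 95% diary adherence in the investigators' earlier studies.

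**The concern.** A likelihood-based mixed model on available data is valid when missingness depends only on what has been recorded. Standard MICE with no offset, followed by the same model, relies on the same condition. If both analyses are wrong about patients who leave, they will tend to be wrong together.

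Item 28 also restricts the imputation to *embedded* gaps, which most naturally means gaps with diary entries on either side. Days after a patient stops for good would then not be imputed at all, although those are the days where a departure from missing at random is hardest to see.

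What is at stake is mainly interpretation. Item 27e presents these analyses as tests of robustness. A close match between the mixed model and the imputed analysis could be published as evidence that missing diary data did not matter, when dropout related to unrecorded pain had not been examined. If such dropout occurred mostly in the oxytocin arm among patients in more pain than predicted, the primary result would favour oxytocin too much. If it occurred in the saline arm, the error would run the other way.

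**Working it through.** **Figures in the plan.** The documents give no missing-data figure to reproduce. The sample-size arithmetic holds: 8/0.38 = 21.1 days, 8/0.47 = 17.0 days, difference 0.09. That difference is in points per day, so it should not be compared with the ln(time) slopes below.

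**How many days are at issue.** Take 120 patients and days 1 to 56, giving 120 × 56 = 6,720 person-days. Day 0 is left out because ln(0) is undefined. If a share of all patients stops at day 14, each loses 42 days:

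| Share stopping (assumed) | Days lost | Share of 6,720 |
|---|---|---|
| 5% | 6 × 42 = 252 | 3.8% |
| 10% | 12 × 42 = 504 | 7.5% |
| 20% | 24 × 42 = 1,008 | 15% |

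On its natural reading, item 28 imputes none of these.

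**Size of the possible shift.** For x = ln(t), t = 1 to 56, the mean is 3.078 and Sxx = 44.2. A constant excess δ on all days after 14 changes a fitted slope by δ × L, where L = Σ(t>14)(x − mean)/Sxx = 17.9/44.2 = 0.405. If a share p of one arm is affected, the between-arm slope difference shifts by p × δ × L:

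- p = 5%, δ = 1: 0.05 × 1 × 0.405 = 0.020 per ln-day
- p = 10%, δ = 2: 0.10 × 2 × 0.405 = 0.081 per ln-day
- same p and δ in both arms: the two terms cancel, giving 0

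**Scale.** The SAP gives only a residual SD below 2.0. Assuming a residual SD of 1.5 and a between-patient slope SD of 0.5, the SE of the slope difference is √[(2/60)(0.5² + 1.5²/44.2)] = 0.100. The shift is then 0.2 to 0.8 SE. For a two-sided 5% test of the slope alone, a bias of that size would raise the error rate to about 5.5% to 12.8%. With slope SDs from 0.3 to 1.0, the SE runs from 0.07 to 0.19, and a shift of 0.08 is about 1.2 down to 0.4 SE.

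**Would the planned check notice?** This was simulated under assumed values: 60 per arm, 56 days, random intercept and ln(time) slope, AR(1) residuals, 5% random embedded gaps, and dropout in the oxytocin arm only, starting between days 11 and 22. There were 100 replicates at 10% dropout and 80 at 20%, with 5 imputations. Variance components were treated as known. The true effect was zero apart from the excess pain δ after dropout. Mean ln(time) slope differences:

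| Dropout, δ | Full data | Mixed model, available data | Embedded gaps imputed | All days imputed, δ = 0 | Dropout days imputed with δ |
|---|---|---|---|---|---|
| 10%, 0 | −0.002 | −0.002 | −0.002 | −0.001 | −0.002 |
| 10%, 2 | 0.089 | 0.006 | 0.006 | 0.006 | 0.088 |
| 20%, 2 | 0.179 | 0.014 | 0.014 | 0.012 | 0.177 |

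The embedded-only imputation differed from the mixed model by about 0.004 to 0.005 per trial, against an SE of about 0.10, and it repeated the mixed model's bias. Imputing the dropout days without an offset did not help either. The last column recovers the full-data value by construction, because the true δ was supplied. In a real trial δ is unknown, which is why a range of values is needed.

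**The case against.** **Dropout is not ignored.** Patients who stop contribute their recorded days, and the likelihood handles the rest under missing at random. This stands. What is missing is a test of that assumption.

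**The scope of the imputation is not settled.** Item 27e says "These are to include multiple imputation for missing data" without limit; only item 28 narrows it, and *embedded* is never defined. A reader might infer that the SAP definitely excludes post-dropout days. The text makes that likely but not certain, so the two items need reconciling.

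**Stopping because of recorded pain is harmless here.** A patient whose diary already shows recovery, or severe pain, and who then stops is still missing at random. Bias needs stopping to depend on pain that was not recorded, given the recorded series. This narrows the concern.

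**The imputation is not a pure duplicate.** It uses each patient's autocorrelation and baseline predictors, while item 27a states no autocorrelated residual structure. A reader might infer that the check must agree with the primary model in all circumstances. The documents do not support that: disagreement could expose sensitivity to residual structure or covariates.

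**Later data may help.** The monthly and 12-month contacts could capture pain in some patients who stopped the diary. They are not specified as a missing-data analysis and do not fill the first 56 days.

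**The effect may be small.** Earlier adherence exceeded 95%, missed entries prompt a call or email, payment is tied to completion, and a single blinded injection gives no obvious reason for dropout to differ by arm. This has weight. An average does not show whether losses are terminal or one-sided, however: 6 patients in one arm stopping at day 14 would cost 6 × 42 = 252 days, only 3.75% of the total.

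**Conclusion.** The concern holds in a limited form. The primary model relies on an unstated missing-at-random assumption for all missing diary days, including those after dropout. The one planned missing-data check relies on essentially the same assumption, so it gives little or no information about dropout that depends on unrecorded pain. Agreement between the two should not be described as robustness to dropout.

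The missing-at-random assumption is inferred from the methods named, since the SAP names none. The size is conditional: about 0.02 to 0.08 per ln-day under assumed one-arm dropout of 5% to 10% at day 14 and a departure of 1 to 2 points, near zero if dropout and departure are balanced between arms, and likely small if adherence matches the figure cited. A reader might infer that the primary result is biased. The documents do not support that, because they give no dropout rate and no evidence that dropout differs by arm or depends on unrecorded pain.

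**What to change.** 1. In item 28, state that the primary model and the standard imputation assume missing at random.
2. Reconcile items 27e and 28. Say that imputation is a sensitivity analysis, define embedded and post-dropout missing days, and impute both through day 56.
3. Add a delta-adjusted analysis in the same MICE step. Shift imputed post-dropout pain by 0, 0.5, 1 and 2 points in the oxytocin arm, in the saline arm, and in both. Report the delta at which the primary conclusion changes, or that it does not change within the range.
4. Report the number of patients who stopped and the day of the last diary entry by arm, so that readers can judge how much the delta table matters.

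The cost is a few lines of code and one extra table. The delta range is a judgement and should be justified briefly. The primary analysis does not change. Item 4 of the SAP says that the revision was made after data acquisition and before unblinding, so the pooled pattern of stopping could be examined without allocation. If the analysis has already been unblinded, label the delta analysis as post hoc.
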